**Principal Investigator (PI):** [name]

**Title of Study:** Right Ventricular Septal Pacing in Patients with Right Bundle Branch Block and Heart Failure, a Pilot Clinical Trial

**Study Center:** University of Iowa

**Estimated number of subjects:** 40 adults over the age of 18

I.	Introduction.....	3
II.	Background .....	5
III.	Statement of Compliance.....	7
IV.	IRB Oversight.....	8
V.	Location of Study Procedures.....	9
VI.	Main Hypothesis.....	10
VII.	Inclusion/Exclusion Criteria .....	11
VIII.	Study Procedures .....	13
IX.	Adverse Event Reporting: .....	14
X.	Data Management.....	17
XI.	Subject Safety .....	18
XII.	References.....	19

## I. Introduction

Heart failure is the fastest growing cardiovascular diagnosis in the United States, with a prevalence of approximately 2.5% in adults. The direct and indirect costs of heart failure exceed \$33 billion per year.

Heart failure condition is commonly associated with abnormalities in the heart electrical conduction system that leads to losing the ability to achieve strong synchronized contractions.

During last decade, Cardiac Resynchronization therapy (CRT) has evolved as one of the standard therapies in heart failure field to target this issue; many large randomized controlled trials showed that this therapy significantly improves symptoms, heart function, rate of hospitalization, and overall mortality.

CRT requires pacemaker implantation in the cardiac catheterization laboratory. Implanted pacemaker activates or pace the heart in a synchronized fashion to minimize the deleterious consequences of the electrical abnormalities that are usually associated with heart failure.

It is well known now that patients with a specific conduction disease called left bundle branch block (LBBB) represent the heart failure group that benefit the most from this therapy, while heart failure patients with right bundle branch block (RBBB), another conduction disease, who represent around 10% to 15% of heart failure patients do not benefit as much.

CRT activates the areas of the heart that is affected mainly by LBBB not RBBB, it requires the addition of an extra leader wire to the regular defibrillator device that heart failure patients usually have, this procedure is usually done in the cardiac catheterization lab and considered as an invasive procedure.

As most patients with moderate to severe heart failure including who have RBBB meet current guidelines recommendations for defibrillator placement to prevent sudden cardiac death, most of them have already a defibrillator that is capable of pacing too and is placed routinely in the area of the heart that can normalize the RBBB associated electrical abnormalities if it would be paced by an appropriately programmed device.

In our proposed clinical trial, we are planning to recruit heart failure patients with only right bundle branch block who have already defibrillator or pacemaker, and after obtaining an informative consent, we will program their pacemaker/defibrillator to provide a novel form of CRT that target RBBB as we mentioned earlier without any need for an invasive procedure.

Our study's design is a randomized controlled single blinded cross-over study. Overall designs will include two 12 weeks treatment periods separated by 8 weeks washout periods.

One group will have pacing-washout-placebo sequence while the other will have placebo-washout-pacing sequence. Subjects will be randomized to either pacing (intervention) or non-pacing (placebo) with 1:1 ratio at the initial visit. Each subject will undergo heart ultrasound (echocardiogram), symptoms/quality of life assessment, and 6 minute walking distance assessment at initial, 12, 20, 32 weeks visits. This type of clinical trial design will have an advantage of blinding the intervention to the subject which will minimize bias and would create a control group. Indeed, will allow still to use relatively small number of subjects with enough power to test outcomes comparable to single arm prospective trial design, while parallel randomized controlled studies design would require higher subjects numbers for reaching an adequate power to test outcomes of interest due to lack of self control.

This study will allow us to evaluate the effect of this intervention on heart failure symptoms, heart size and function as well as quality of life in this specific group of heart failure patients.

## II. Background

Several randomized trials and meta-analyses (1,2,3,9,10) conducted within the last decade showed that bi-ventricular cardiac resynchronization therapy (BIV-CRT) is an effective therapy for heart failure (HF) patients with LVEF=<35% and NYHA class III and IV symptoms who are on optimal medical therapy and have left bundle branch block (LBBB) with or without ICD. Most recently, some studies have shown that BIV-CRT benefits extend to HF patients that are less symptomatic [NYHA class I and II symptoms].(8,9) BIV-CRT significantly decreases all-cause mortality and cardiovascular morbidity including a reduction in heart failure hospitalizations, and it is associated with remarkable symptomatic improvement in HF patients at short term. Reverse positive remodeling represented by the decrease in left ventricular (LV) size, improvement of intra- and inter-ventricular synchrony and eventually improvement in LV function is the main mechanism of action of this therapy.

Many studies showed that the presence of right bundle branch block (RBBB) in patients with cardiovascular disease is associated with worse cardiovascular outcomes (4). Overall, RBBB prevalence in HF population according to previous studies ranges from 10-15% (3,9).

It is well known from previously conducted studies that BIV-CRT is most effective in patients with LBBB and that non-LBBB patients including RBBB patients tend to be overall non-responders with similar outcomes profile of the patients who underwent only ICD implantation(3,5,11). Studies have linked the response to CRT to the presence of the left intra-ventricular and/or inter-ventricular desynchrony which are common in LBBB patients(2,14). Indeed, patients who did show some response to BIV-CRT in the RBBB group were more likely to have left-sided dyssynchrony (6), left sided conduction disease (15), non-LAFB conduction pattern (5) or prolonged PR interval >230 ms (7). In the last scenario, the response was likely due to the correction of atrio-ventricular dysynchrony.

RBBB is associated with wide QRS and often with wall motion abnormalities and inter-ventricular dyssynchrony. Right sided intra-ventricular dyssynchrony or conduction delay is common and significant which can be accompanied sometimes by also left sided dyssynchrony(6,14). If those abnormalities can be minimized by a specific right sided pacing therapy, it may potentially result in reverse right ventricular remodeling and secondary left ventricular remodeling interventricular interdependence phenomenon which may lead to an improvement in cardiac output and hemodynamics as BIV-CRT does in LBBB situation.

RBBB patients have an intact conduction through the left bundle branch, thus pacing only the right ventricle targeting just the diseased right bundle branch and utilizing the normal conduction through left system may work better than pacing both ventricles together or only Left ventricle (14). By optimizing atrio-ventricular delay interval setting when programming the pacemaker/ICD, we can achieve a narrow fused ventricular activation wave (QRS complex) in RBBB patients that results from fusion of both the pacemaker wave and the normally conducted intrinsic wave through the intact left bundle branch. This may restore the normal ventricular activation sequence and hence we may achieve the wished effects described above.

Placement of the right ventricular (RV) lead tip varies in location between the RV apex and the mid portion of the septum. We do expect that mid septal location of RV lead (or sometimes called right ventricular outflow "RVOT" lead) would result in better fusion of ventricular activation waves (13) and thus will be likely more effective in restoration of the electrical and mechanical synchrony than apical RV leads. Apical lead not uncommonly creates iatrogenic LBBB that can be sometimes of deleterious effect on HF patients. Current practice has shifted toward septal lead placement, but apical leads are still common. Our study will include both types of RV lead location and will hopefully add some insight into this.

We are currently publishing interesting data which shows that right ventricular pacing in RBBB patients by mid septal leads can significantly reduce QRS duration and achieve narrow fused QRS waves(12). Also, we are working on case series to report the effect of this pacing intervention on normalizing wall motion abnormalities associated with RBBB by echocardiogram.

We believe that this is an attractive pacing therapy for heart failure that is worthy of further study; we hypothesize that using only a single RV lead in HF patients with RBBB and has LVEF=<35% would improve heart failure symptoms by inducing reverse remodeling process and likely have a significant impact on cardiovascular outcomes, hopefully similar to those seen with BIV-CRT in HF patients with LBBB.

Our proposed study will be the first on this topic, as no published clinical trials can be found in the literature using this technique of CRT therapy. We expect that if we can prove that such intervention leads to positive remodeling and HF symptom improvement that would create interest in proceeding with a large multi-center randomized clinical trial to test this therapy's effect on major cardiovascular outcomes which may lead to major changes in the current guidelines of the pacing therapies in heart failure.

Tens to hundreds of thousands of heart failure patients in the United States who are not candidates for current conventional BIV-CRT due to the presence of RBBB, already have a right ventricular lead as part of their defibrillator implanted for sudden cardiac death prevention and may benefit from such intervention if we find it is effective. Our proposed intervention requires only a simple re-programming of their device' in other means we would provide potentially an added therapy to be delivered by devices that have already been implanted for another indications. Known current BIV-CRT therapy is associated with significant survival gain. Later studies have quantified this gain by analyzing multiple landmark CRT trials; Finegold JA et al as an example found that the number needs to treat (NNT) to save one life is 15 at 3 years in RAFT trial, which represents a breakthrough in medicine. This huge survival benefit that requires only low number of patients to be treated to save lives makes us excited to proceed with our proposed trial.

### **III. Statement of Compliance**

This study will be conducted in compliance with the protocol, Good Clinical Practice and the applicable Food and Drug Administration and other Department of Health and Human Services regulatory requirements.

All key personnel (all individuals responsible for the design and conduct of this study) have completed Human Subjects Protection and Good Clinical Practice training.

## **VI. Main Hypothesis**

To determine whether cardiac resynchronization therapy by single right ventricular lead in heart failure patient with RBBB will be associated with positive reverse left ventricular remodeling and improvement in heart failure symptoms and quality of life.

Primary endpoint Positive reverse left ventricular remodeling, defined as increase in LV Ejection Fraction  $>15\%$  from baseline at 6 months.

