Cover Page for Statistical Analysis Plan

Sponsor-Investigator:	[name]
NCT Number:	NCT02441101
Unique Protocol ID:	201409760
Official Title:	Right Ventricular Septal Pacing in Patients With Right Bundle Branch Block and Heart Failure (The SPARK Trial)
Date of Document:	24 December 2014

Linear mixed model analysis for repeated measures will be used to test for change over the follow-up period in the primary outcome measures. Post-hoc pairwise comparison with baseline will be performed using Dunnett's test. Mean estimates at each time point, and mean change from baseline (with 95% confidence limits) will be computed from the fitted model. All tests were two-tailed and a $p < 0.05$ was considered as statistically significant. All analyses will be conducted using the intention-to-treat population.

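### The primary endpoint is a >15% LVEF criterion, but the SAP analyses only means against baseline and never evaluates that criterion

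*Protocol*

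**What the plan says.** Protocol section VI names one primary endpoint: "Positive reverse left ventricular remodeling, defined as increase in LV Ejection Fraction" above 15% "from baseline at 6 months". It does not say whether 15% means a relative rise or 15 LVEF points, or whether the criterion applies to each subject or to the group.

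The SAP is a single paragraph. Its main analysis is stated as: "Linear mixed model analysis for repeated measures will be used to test for change over the follow-up period in the primary outcome measures". It adds: "Post-hoc pairwise comparison with baseline will be performed using Dunnett's test". The output is described as: "Mean estimates at each time point, and mean change from baseline (with 95% confidence limits) will be computed from the fitted model". The only decision rule is: "All tests were two-tailed and a $p < 0.05$ was considered as statistically significant".

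The SAP does not name LVEF. I take it to be the variable modelled, because it is the only one that section VI makes primary. The 15% figure does not appear in the SAP, and neither document plans a responder variable, a proportion, or a method for binary data.

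The Protocol's front matter gives a planned size of "40 adults over the age of 18", without a derivation. The Introduction describes a two-period crossover: "Subjects will be randomized to either pacing (intervention) or non-pacing (placebo) with 1:1 ratio at the initial visit". Echocardiograms are due at the initial visit and at weeks 12, 20 and 32.

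**The concern.** A threshold definition and a model of means answer different questions: how many patients improved by a set amount, and how far the average moved. The plan defines the first and analyses only the second.

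Two things are at stake. First, the trial could finish with a complete analysis and no result for its one named primary endpoint. Second, a responder definition and a mean model would both be on file with no stated order between them. A reader could not tell which was meant to carry the conclusion, and the choice could be made after the data are seen.

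**Working it through.** **Step 1. Set endpoint and analysis side by side.**

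| | Protocol section VI | SAP |
|---|---|---|
| Quantity | LVEF rise above a threshold | Mean, and mean change |
| Reference value | 15% | Zero change from baseline |
| Time | 6 months | Every follow-up time point |
| Summary | Not stated; proportion if per subject | Means with 95% limits |

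- *Per-subject reading:* the SAP classifies no one as a responder and compares no proportions.
- *Group-mean reading:* the SAP estimates the mean change, but tests it against zero and specifies no comparison with 15%.

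Neither reading is evaluated. Six months is about week 26, which lies between the week 20 and week 32 visits, so no echocardiogram falls there either.

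**Step 2. How small a mean change would be significant?** The documents give no SD, effect size or power, so there is no plan figure to reproduce. What follows is an illustration.

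- From the documents: n = 40; two-sided 0.05; three follow-up times compared with baseline.
- Assumed: SD of within-subject LVEF change 5 to 8 points; change normally distributed; baseline LVEF 28% (the inclusion criteria cap it at 35%).

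Unadjusted: t(0.975, 39) × SD / √40 = 2.023 × SD / 6.325.

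Dunnett: 2.378 × SD / 6.325. The critical value 2.378 was simulated for three comparisons with baseline and about 117 degrees of freedom.

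| SD (points) | Unadjusted | Dunnett |
|---|---|---|
| 5 | 1.60 | 1.88 |
| 6 | 1.92 | 2.26 |
| 8 | 2.56 | 3.01 |

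**Step 3. Compare with the threshold.**

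- *Absolute (15 points):* 1.60/15 = 11% up to 3.01/15 = 20% of the threshold.
- *Relative (0.15 × 28 = 4.2 points):* 1.60/4.2 = 38% up to 2.56/4.2 = 61% unadjusted; 1.88/4.2 = 45% up to 3.01/4.2 = 72% with Dunnett.
- *Extreme case:* at SD 10 and baseline 25%, the relative threshold is 3.75 points. The smallest significant mean is 3.2 unadjusted and 3.76 with Dunnett, so the adjusted gap disappears.

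**Step 4. Responder share at the unadjusted just-significant mean,** as P(Normal(mean, SD) > threshold):

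| Reading | SD 5 | SD 8 | No true change (SD 5, SD 8) |
|---|---|---|---|
| Relative, > 4.2 | 30% | 42% | 20%, 30% |
| Absolute, > 15 | 0.4% | 6% | 0.1%, 3% |

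**Step 5. Could 40 subjects carry the responder endpoint?** Exact McNemar power, 40 completers, two-sided 0.05, responses assumed independent within subject. For 30% on pacing against 10% off, the discordant probabilities are 0.30 × 0.90 = 0.27 and 0.10 × 0.70 = 0.07, so 40 × 0.34 = 13.6 discordant pairs are expected.

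| Assumed rates (pacing, non-pacing) | Power |
|---|---|
| 30%, 10% | 0.51 |
| 40%, 20% | 0.40 |
| 50%, 20% | 0.74 |
| 40%, 10% | 0.84 |

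**The case against.** The strongest reply is that section VI never mentions responders, proportions or individual subjects. If 15% was meant as a group-mean criterion, the SAP's mean change with its 95% limits bears directly on it. This stands in part: the yes/no reading is the natural one but is not certain. It does not rescue the plan, because the planned null is zero change and no comparison with 15% is specified.

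A second reply is that a linear model can be fitted to a 0/1 response. But a response defined as change from baseline is zero for everyone at baseline, so the SAP's comparisons with baseline would not be meaningful for it.

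Third, the figures in steps 2 to 4 treat all 40 subjects as one sample. With 1:1 sequence allocation, about 20 are in a pacing period at week 12 and the other 20 at week 32, so a pooled change from baseline is not a pacing effect. This stands. The figures show the scale of what the planned comparisons could call significant, not the size of a treatment effect.

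Fourth, this is a pilot meant to prompt a larger trial. That bears on how much power to ask for, but not on whether the primary endpoint is analysed.

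A reader might go further and infer that the plan lets success be declared on a mean far below the threshold, with few subjects meeting the definition. The documents do not support that. They state no success rule beyond p < 0.05. The mean is far below the threshold only on the absolute reading, which they do not select. On the relative reading, 30% to 42% would still be responders.

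**Conclusion.** The mismatch is established from the text alone and needs no assumed figure: the plan evaluates its 15% criterion in no form, so following it exactly gives no result for the sole named primary endpoint. This is more than a missing detail, and it should be corrected before analysis.

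The size of the gap between significance and threshold is conditional on the assumed SD and, for the relative reading, on the assumed baseline. It is large if 15% means LVEF points, and moderate and sensitive to the SD if 15% is relative. That the headline might be chosen after seeing the data is a risk the wording leaves open; nothing in the documents shows such an intention.

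**What to change.** Preferred:

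1. In Protocol section VI, make the primary endpoint continuous LVEF, in percentage points, at the end of each 12-week treatment period (weeks 12 and 32). This replaces the 6-month time point, at which no visit falls.
2. In the SAP, make the primary test the pacing versus non-pacing contrast from the mixed model, with fixed effects for treatment, period and sequence and a random subject effect. Rewording section VI alone is not enough, because the SAP names no such contrast and no period or sequence term.
3. Keep the >15% response as a named secondary endpoint. State that it applies per subject and whether it is relative or absolute. Compare it within subject by a method that allows for period: mixed logistic regression, GEE, or the Mainland-Gart test. Plain McNemar ignores period effects.

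Alternative: keep the >15% response as primary, define it as in item 3, and add that within-subject analysis to the SAP.

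Cost: a wording change in section VI and a short rewrite of the SAP paragraph. No new data are needed, as the week 12 and week 32 echocardiograms are already scheduled. Under the preferred option the headline becomes a mean difference rather than a responder rate. Under the alternative, power is low with 40 subjects unless the difference in responder rates is about 30 percentage points or more (step 5).

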## **VII. Inclusion Criteria**

Our subject population is one group of patients who has the diagnosis of systolic heart failure.

Inclusion criteria:

Cardiomyopathy, ischemic or non-ischemic on optimal medical therapy per current heart failure treatment guidelines for at least 3 months.

LVEF <=35% by echocardiogram

Prior implantation of pacemaker/defibrillator with at least atrial and RV mid septal leads. Atrial lead can be waived if RV lead has atrial sensing capabilities.

Presence of right bundle branch block (RBBB), with QRS duration =>120 msec

Normal sinus rhythm

PR interval <250 msec on surface EKG

-Note: Subjects with Biventricular pacemaker/ICD will be enrolled if their LV lead has been deactivated by the their primary cardiologist prior to study enrollment for at least 3 months (this could be due to lead malfunction or the decision to deactivate the biventricular pacing therapy for any reason per primary cardiologist discretion)

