## VIII. Study Procedures

After informative consent signed by potential subject and at the same visit (initial visit), every subject will undergo pacemaker/defibrillator screening check, transthoracic echocardiogram if no echocardiogram available within 6 months preceding the initial visit, and pregnancy test for females whose age 18-50 year-old, if subject is deemed still eligible based on the results of this initial visit screening tests, he/she will be randomized to one of the study's arm and undergo the following baseline tests/procedures.

Initial visit baseline tests/procedures:

A- 6-minute walking test if subject has not had one within 3 months prior to enrollment.

B- Subject will be requested to fill two questionnaires:

- 1- "Minnesota living with heart failure" questionnaire to assess your quality of life
- 2- "Self-assigned New York Heart Association survey (SA-NYHA)" to evaluate the severity of your heart failure symptoms.

C- Medications review, vital signs (heart rate, blood pressure measurement, and weight)

D Baseline pre- and post-programming 12 leads EKG

E- Pacemaker/defibrillator programming session will be performed on all subjects.

Patient assigned to the arm that start with pacing initial treatment period, their devices will be programmed according to our study protocol for RBBB pacing therapy.

After the initial visit, subject will be scheduled for follow up visits. Each visit will last approximately (60-120 minutes) and will be located at University of Iowa Heart and Vascular center –adult outpatient facilities where each subject will have the following tests performed:

A-Follow up trans-thoracic echocardiogram

B-Follow up 6-minute walking test

C-Subject will be requested to fill the two-questionnaire mentioned above again for follow up purposes.

D-Medications review, follow up vital signs (heart rate, blood pressure measurement, and weight)

E-Subject will be asked whether has been hospitalized, has had any medication changes, or has suffered any acute myocardial infarction or stroke/TIA for the preceding 3 months.

F- Blood draw for laboratory tests (Sodium, BUN, Cr, and NT-proBNP)

G-Baseline pre- and post-programming 12 leads EKG

H-Follow up pacemaker/defibrillator check

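### The primary endpoint is set at 6 months, when no echocardiogram is scheduled, and the SAP neither assigns it to a visit nor compares pacing with non-pacing

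*Protocol*

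**What the plan says.** - **Endpoint.** Protocol Section VI defines positive remodelling as an LVEF increase above 15% "from baseline at 6 months".
- **Design.** Protocol Section I: "Overall designs will include two 12 weeks treatment periods separated by 8 weeks washout periods". It continues: "One group will have pacing-washout-placebo sequence while the other will have placebo-washout-pacing sequence".
- **Echo schedule.** The sentence in Section I that schedules the echocardiogram and the symptom and quality-of-life assessments ends "6 minute walking distance assessment at initial, 12, 20, 32 weeks visits".
- **Reason for a small sample.** Section I argues that a parallel-group trial "would require higher subjects numbers for reaching an adequate power to test outcomes of interest due to lack of self control".
- **Entry.** Section VII requires "LVEF <=35% by echocardiogram".
- **Visits.** Section VIII says "After the initial visit, subject will be scheduled for follow up visits". It lists an echo at each but gives no weeks. At screening it asks for a "transthoracic echocardiogram if no echocardiogram available within 6 months preceding the initial visit".
- **Analysis.** The SAP is one paragraph. It plans a repeated-measures linear mixed model for change during follow-up, Dunnett comparisons of later time points with baseline, model means and mean changes with 95% limits, and an intention-to-treat population. It mentions no visit week, 6-month time point, treatment term, period term or sequence term.

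**The concern.** A primary endpoint needs a time at which it is measured, and this one has none. The neighbouring echoes answer different questions. At week 20 both sequences are at the end of washout. At week 32 they are on opposite assignments, reversed from week 12.

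The SAP does not close the gap. It compares time points with baseline and names no contrast between pacing and non-pacing. At weeks 12 and 32 the subjects, taken together, are a mixture of paced and unpaced.

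Two things are at stake. The visit and contrast that carry the primary result could be settled after LVEF has been seen at three follow-up visits. And a report in the words of Section VI would claim a 6-month effect in a trial that assigns each subject 12 weeks of pacing.

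**Working it through.** **1. Visit times (Protocol Section I).** 12, then 12 + 8 = 20, then 20 + 12 = 32 weeks. With the initial visit this reproduces the stated schedule of 0, 12, 20 and 32 weeks exactly.

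**2. Six months in weeks.** 365.25/2 = 182.6 days = 26.1 weeks; with 4-week months, 24 weeks. Neither is a visit, and both lie between week 20 (day 140) and week 32 (day 224).

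**3. A nearest-visit rule does not settle it.**

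| 6 months taken as | Days from week 20 | Days to week 32 | Nearest |
|---|---|---|---|
| 182.625 days | 42.625 | 41.375 | week 32, by 1.25 days |
| 182 days | 42 | 42 | tie |
| 180 days | 40 | 44 | week 20 |
| 168 days (24 weeks) | 28 | 56 | week 20 |

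**4. Exposure at 6 months.** Pacing-first subjects have been off study pacing for 24 − 12 = 12 to 26.1 − 12 = 14.1 weeks. The others have had 24 − 20 = 4 to 26.1 − 20 = 6.1 of their 12 weeks (33% to 51%). Reading 6 months as total treatment time (12 + 12 = 24 weeks) does not help, because only half of that is pacing.

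**5. What change from baseline estimates.** Let d be the 12-week pacing effect on mean LVEF, and m12 and m32 the mean changes that would occur without pacing. Assume equal sequences and no carry-over. Pooled over sequences:

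- week 12: m12 + d/2
- week 32: m32 + d/2

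So the test can be positive with d = 0 if m12 or m32 is not zero, for example through regression to the mean after entry on a low LVEF. With m12 = m32 = 0 it shows only half of d. The within-subject contrast recovers d. Half the difference between sequences in (week 12 − week 32) is ½[(m12 + d − m32) − (m12 − m32 − d)] = d.

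**6. Illustration: one visit against both period ends.** Assume 20 per sequence (40 is the protocol's estimated total), complete data, no carry-over, standard deviation s and within-subject correlation r. Variance of the LVEF treatment estimate:

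- both period ends: s²(1 − r)/20
- one visit, baseline as covariate: s²(1 − r²)/10. The ratio is 2(1 + r) = 3.0 at r = 0.5 and 3.6 at r = 0.8, so the standard error is 1.73 to 1.90 times as large.
- one visit, change from baseline: s²(1 − r)/5. The ratio is 4, so the standard error is 2.0 times as large.

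For a responder outcome I simulated 20,000 trials per row (latent normal correlation 0.5, t test with 38 df). The documents give no responder rates, so these are assumed:

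| Non-pacing v pacing | Both period ends | One visit |
|---|---|---|
| 15% v 40% | 84% | 44% |
| 15% v 30% | 46% | 20% |
| 15% v 25% | 24% | 12% |

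Type I error of the linear model on 0/1 data, using both period ends, is close to nominal at a 15% responder rate (4.5%). It falls to about 3% at a 5% rate and 0.5% at 2%.

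**7. Baseline and carry-over, mean LVEF only.** Let c and c′ be the shares of the pacing effect left at weeks 20 and 32 in pacing-first subjects. The bias as a share of d is −c′/2 with a week 0 baseline and +(c − c′)/2 with period baselines (weeks 0 and 20). Under assumed exponential decay, c = 0.5^(8/h) and c′ = 0.5^(20/h) for half-life h:

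| Half-life | Week 0 baseline | Period baselines |
|---|---|---|
| 4 weeks | −1.6% | +10.9% |
| 8 weeks | −8.8% | +16.2% |
| 12 weeks | −15.7% | +15.7% |

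**8. Threshold.** At LVEF 35%, a relative 15% is 0.15 × 35 = 5.25 points; an absolute 15% is 15 points.

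**The case against.** The best defence is that the SAP picks no single visit. It plans a model over all visits, so the loss in step 6 belongs to an analysis that nobody has proposed. That stands. A reader might infer from step 6 that the trial plans a comparison of 20 with 20, or that its power falls from 84% to 44%. The documents support neither: they contain no one-visit test, responder rate, standard deviation or correlation, and the size of the loss changes with the assumed rates. Nor does 84% show that the corrected analysis is adequately powered, since smaller assumed effects give 46% or 24%.

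It is also fair to say that the missing treatment contrast is a separate omission from the time label. But correcting the label alone would leave a primary test that does not estimate the effect of pacing, so the two need to be settled together.

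The trial is a pilot meant to prompt a larger one. That lowers what is asked of its power. It does not remove the need for a primary endpoint that can be measured.

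Finally, fitting a linear model to a 0/1 responder is not the obvious remedy. It becomes very conservative at low rates, which are plausible if 15% means LVEF points. That objection is accepted in the fix.

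**Conclusion.** The inconsistency is established from the documents and rests on no statistical assumption. The primary endpoint has no echo at its stated time under any usual conversion of 6 months, and pacing is assigned for 12 weeks at most. As written, the SAP has no contrast that isolates pacing. This should be settled before analysis.

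A stronger reading would be that the trial cannot answer its question. The documents do not support that: the echoes at weeks 12 and 32 give each subject one reading under each assignment. What the schedule cannot show is a 6-month pacing effect, and the documents do not say whether that was the intent.

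The standard-error ratios and power figures are illustrations under the stated assumptions. The carry-over percentages apply to mean LVEF and not to a responder difference.

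**What to change.** Reconcile Protocol Sections I, VI and VIII with the SAP before analysis. With the schedule as it stands:

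1. **Section VI.** Replace the 6-month time point with the end of each 12-week treatment period (weeks 12 and 32) and describe the result as a 12-week effect. State whether 15% is relative or in LVEF points.
2. **SAP, contrast.** Make pacing versus non-pacing within subject at weeks 12 and 32 the primary contrast. Take it from the planned linear mixed model with treatment, period and sequence terms and a random subject effect. The Dunnett comparisons with baseline become descriptive.
3. **SAP, outcome form.** Name one in advance: LVEF in the mixed model, or the responder indicator with a paired crossover test that holds up at low responder rates.
4. **Baseline.** Prespecify the week 0 value, with period baselines as a sensitivity analysis. Reconcile Section VIII, which lets an echo up to 6 months old stand in at screening, with Section I, which has an echo at the initial visit.
5. **Population.** Analyse subjects as randomised. If at least one period-end echo is required, call that a modified intention-to-treat set.

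**Cost.** A short amendment and a changed primary contrast. The claim is limited to 12 weeks, and carry-over still present at week 32 would understate the effect. No visits are added, but some initial-visit echoes that Section VIII would have waived may be needed.
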